Variables	Data on demographics, clinical characteristics, and treatment regimens, among others, will be collected. Healthcare resource utilization will be captured to understand the management pattern of both patient populations.
Data sources	All data will be extracted from patients' medical charts and entered into an electronic case report form (CRF) specifically designed to capture relevant information in accordance with the study outcomes
Study size	It is expected the study will enroll approximately 700 patients with B-cell ALL R/R and AML in a consecutive manner, in approximately 15 sites distributed across Argentina, Brazil, Chile, and Colombia
Data analysis	All relevant data reported in the medical chart since diagnosis date (index date) until the study enrollment, last visit, contact date or death, whichever comes earlier, will be assessed. Follow-up period, time to next treatment (TTNT), overall survival (OS), relapse-free survival (RFS), event-free survival (EFS) will be assessed.
Milestones	
- CRF and electronic CRF (eCRF): June 2021- Study documents (data management plan, data validation plan, statistical analysis plan): May 2021- Start of data collection: July 2021- End of data collection: August 2022- Data analysis: August 2022- Final study report: November 2022

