9.7. Data Analysis

Detailed methodology for summary and statistical analyses of data collected in this study will be documented in a statistical analysis plan (SAP), which will be dated, filed and maintained by the sponsor. The SAP may modify the plans outlined in the protocol; any major modifications of primary endpoint definitions or their analyses would be reflected in a protocol amendment.

Analyses will be descriptive in nature, as no hypothesis is being tested. Disease staging, comorbidities, demographic, clinical characteristics will be described at the date of diagnosis and/or treatment initiation for patients diagnosed with B-cell ALL R/R or AML. Treatment and clinical information will be assessed up to the most recent data available at the study enrollment. The treatments will be described in sequence according to the chronological order of administration. The duration through the number of cycles will be evaluated. Dose reduction information will also be collected.

Continuous variables will be described as mean and standard deviation (SD), and/or as median, minimum, maximum, interquartile range (IQR, 25th and 75th percentiles).

Categorical variables will be described by simple and cross contingency tabulation, with absolute frequencies and percentages. Missing values will be included in the denominators for the calculation of percentages and missing categories will be presented.

All time-to-event analysis will be described using a Kaplan Meier plot, if appropriate. The following definition and parameter analysis will be considered:

- Follow-up period – considered the time elapsed since B-cell ALL R/R or AML diagnosis until the study enrollment. It will be presented in years.
- Time to next treatment (TTNT) – considered as the time from the start date of the front-line therapy to the start date of a subsequent line of therapy. It will be presented in months.
- Overall survival (OS) – considered as death from any cause from the time of initiation of diagnosis or treatment.^{70,71} The median overall survival (OS) and the % of alive patients in 1, 3- and 5-years follow up of newly diagnosed AML and relapsed/refractory B-cell ALL patients will be assessed.

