- Relapse-free survival (RFS) for newly diagnosed AML patients – considered as measured from the date of achievement of a remission until the date of relapse or death from any cause; patients not known to have relapsed or died at last follow-up are censored on the date they were last examined. Defined only for patients achieving CR, or CRI.

- Event-free survival (EFS) of newly diagnosed AML and relapsed/refractory B-cell ALL patients – considered as the measured from the date of initiation of treatment to the date of primary refractory disease, or relapse from CR, or CRi, or death from any cause; patients not known to have any of these events are censored on the date they were last examined

All computations and generation of tables, listings, graphics, and data for figures will be performed using R® version 3.5.3 or newer version (R Core Team), or a comparable statistical software package.

Medical Dictionary for Regulatory Activities Terminology (MedDRA) version 2.1 (V2.1) or newer version will be used as a standardised medical terminology. Medicinal product names will be codified using World Health Organisation Drug Dictionary (WHODrug), a dictionary maintained and updated by Uppsala Monitoring Centre (UMC).

The resource utilization (eg, number of hospital admissions, hospitalization period, procedures during hospital admissions) will be presented as mean number per patient per year (PPPY). According to the sample distribution, the data will be presented with a standard deviation (SD) or a 95% confidence interval (95% CI), which will be estimated either by Poisson regression or Gama distribution. The PPPY will be calculated as the sum of all event observed in the cohort divided by the total follow-up period (in years) of all patient in the cohort (including those who did not present the event).

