8.2. Setting

8.2.1. Study Time Period

For this study, data from patients treated at public or private healthcare facilities in Argentina, Brazil, Chile, Colombia, diagnosed with R/R B-cell ALL or AML between 01 January 2015 and 31 December 2019 will be considered for the analysis.

The eligibility period of 5 years was determined to increase the overall patient representativeness, and to allow ample follow-up to assess survival outcomes.

The study will be conducted in approximately 15 sites distributed across Argentina, Brazil, Chile, and Colombia, and is expected to enroll approximately 700 patients with R/R B-cell ALL and AML in a consecutive matter. To assure the representativeness of each country, the number of sites and the total expected enrolled patients will be limited according to the country, considering the prevalence/incidence of the diseases.

Data collection will occur in a period of up to 12 months following the independent ethics committee (IEC)/ institutional review board (IRB) approval and study set up. Patients will be consecutively enrolled, considering both target population, with no set proportion of AML and R/R B-cell ALL patients to be included in the study. However, it is expected a higher proportion of AML patients in the cohort. The study period will comprise since diagnosis date (index date) until the study enrollment or death, whichever comes earlier.

[figure not shown]

Figure 1. Study time period.

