8.7. Data Analysis

Analyses will be descriptive in nature, as no hypothesis is being tested. Disease staging, comorbidities, demographic, clinical characteristics will be described at the date of diagnosis and/or treatment initiation for patients diagnosed with B-cell ALL R/R or AML. Treatment and clinical information will be assessed up to the most recent data available at the study enrollment. The treatments will be described in sequence according to the chronological order of administration. The duration through the number of cycles will be evaluated. Dose reduction information will also be collected. All analysis, including subgroup assessment, will be performed according to the data availability.

Continuous variables will be described as mean and standard deviation (SD), and/or as median, minimum, maximum, interquartile range (IQR, 25th and 75th percentiles). Categorical variables will be described by simple and cross contingency tabulation, with absolute frequencies and percentages. Missing values will be included in the denominators for the calculation of percentages and missing categories will be presented.

Follow-up period will be considered the time (in years) elapsed since B-cell ALL R/R or AML diagnosis until the study enrollment. It will be summarized as a continuous variable.

All time-to-event analysis will be described using Kaplan Meier methods and plots, if appropriate. The following definition and parameter analysis will be considered:

- Time to next treatment (TTNT) – considered as the time from the start date of the front-line therapy to the start date of a subsequent line of therapy. Patients without a subsequent line of therapy will be censored at study enrollment, last visit, last contact, or death, whichever comes first. It will be presented in months.
- Overall survival (OS) – considered as death from any cause from the time of initiation of diagnosis or treatment [12,13]. Patients not known to have died will be censored at study enrollment, last visit, last contact, whichever comes later. The median OS and, if feasible, the % of alive patients in 1, 3- and 5-years follow up of newly diagnosed AML and R/R B-cell ALL patients will be assessed.

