- Relapse-free survival (RFS) for newly diagnosed AML patients – considered as the date of achievement of a remission until the date of relapse or death from any cause; patients not known to have relapsed or died at last follow-up are censored on the date they were last examined, study enrollment, last contact, whichever comes later. Defined only for patients achieving CR, or CRI. The RFS will be measured as the treatment end date until next treatment initiation or date of death, whichever comes first, for all AML patients who achieved Complete remission/response (CR) or Complete remission/response with incomplete hematological/count recovery (CRI) at the end of treatment.
- Event-free survival (EFS) of newly diagnosed AML and R/R B-cell ALL patients – considered as the date of initiation of treatment (or date of diagnosis, if the previous is not available) to the date of primary refractory disease, or relapse from CR, or CRI, or death from any cause; patients not known to have any of these events are censored on the date they were last examined, study enrollment, last contact, whichever comes later. The EFS will be measured as the time since AML and R/R ALL initiation of treatment (or newly AML diagnosis and newly ALL diagnosis, if treatment date is not available) until i) treatment end date (or treatment start date of the next treatment line, if the previous is not available) when treatment response was Refractory disease(5) or Relapsed from CR or CRI or recurrent disease(6) as treatment response; ii) date of death, whichever comes first.
 - Clinically relevant events:
 - Hematological toxicities
 - Hepatotoxicity
 - Gastrointestinal toxicities
 - Tumor lysis syndrome
 - Fatigue
 - Dysgeusia
 - Alopecia
 - Muscle spasms
 - Infections

- Sepsis
- Secondary malignancy due to drug toxicity
- Death
- Other

Medical Dictionary for Regulatory Activities Terminology (MedDRA) version 2.1 (V2.1) or newer version will be used as a standardised medical terminology. Medicinal product names will be codified using World Health Organisation Drug Dictionary (WHODrug), a dictionary maintained and updated by Uppsala Monitoring Centre (UMC).

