 - Hepatotoxicity.
- Most common adverse events description

7. To each newly AML and R/R B-cell ALL patients, the EFS will measure time since the date of initiation of treatment (or newly AML diagnosis and newly ALL diagnosis, if the previous is not available) until i) treatment end date (or treatment start date of the next treatment line, if the previous is not available) when treatment response was Refractory disease(5) or Relapsed from CR or CRI or recurrent disease(6); i) date of death, whichever comes first. This time-to-event analysis will be described summarized in tables and using Kaplan Meier methods and plot, if appropriate. Patients not known to have any of these events are censored on the date they were last examined:

newly AML

- Descriptive (median and CI(95%) estimations of Kaplan-Meier) of EFS;
- Time categorized count and percentages.

R/R B-cell ALL

- Descriptive (median and CI(95%) estimations of Kaplan-Meier) of time between treatment initiation and R/R event in months;

- Time categorized count and percentages.

8. The OS will be measure for both newly AML and R/R B-cell ALL patients as median time since newly diagnosis or treatment initiation until death from any cause. This time-to-event analysis will be described using a Kaplan Meier plot, if appropriate

newly AML

- Descriptive (median and CI(95%)) estimations of Kaplan-Meier) of time between date of diagnosis or treatment initiation and R/R event in months;
- Time categorized count and percentages.

This analysis will also be described for fit and non-fit newly AML patients.

R/R B-cell ALL

- Descriptive (median and CI(95%)) estimations of Kaplan-Meier) of OS;
- Time categorized count and percentages.

9. The median OS and the percentage (and 95% confidence intervals) of alive patients in 1, 3- and 5-years, if feasible, follow up of newly diagnosed or treatment initiation AML and R/R B-cell ALL patients will be assessed. The OS will be defined as median time since newly diagnosis or treatment initiation until death from any cause. This time-to-event analysis will be described using a Kaplan Meier plot, if appropriate.

newly AML

- Descriptive (median and CI(95%)) estimations of Kaplan-Meier) of time between treatment initiation and death in months;
- Time categorized count and percentages.

This analysis will also be described for fit and non-fit newly AML patients

R/R B-cell ALL

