- Descriptive (median and CI(95%)) estimations of Kaplan-Meier) of time between treatment initiation and death in months;
- Time categorized count and percentages.

10. For all AML patients who achieved Complete remission/response (CR) or Complete remission/response with incomplete hematological/count recovery (CRI) at the end of treatment, the RFS analysis will consider the treatment end date until date of next treatment initiation or date of death, whichever comes first. This time-to-event analysis will be described using a Kaplan Meier plot, if appropriate.

newly AML

- Descriptive (median and CI(95%)) estimations of Kaplan-Meier) of RFS
- Time categorized count and percentages.

11. For newly AML patients, each treatment response (induction and consolidation therapy) will assess the proportion of patients who achieve complete remission (CR), complete remission with incomplete haematological recovery (CRI), complete remission without minimal residual disease (MDR-), partial remission (PR), and progressive disease. No statistical testing will be carried out. Only descriptive data will be reported (absolute number, frequency, mean \pm standard deviation, median, interquartile range, minimum or maximum) for.

Newly AML patients:

- Treatment response
 - CR,
 - CRI,
 - partial remission/response,
 - progressive disease,
 - refractory disease,
 - relapsed from CR or CRI or recurrent disease,
 - other
- Minimal residual disease (MRD) evaluation for patients that achieved CR or CRI and the diagnose method for MRD evaluation
- Patient status description

12. For R/R B-cell ALL patients, each treatment response (to rescue treatment) will access the proportion of patients with complete remission (CR), complete remission without minimal residual disease (MRD-), partial remission (PR), and progressive disease. No statistical testing will be carried out. Only descriptive data will be reported (absolute number, frequency, mean ± standard deviation, median, interquartile range, minimum or maximum) for.

R/R B-cell ALL patients:

- Treatment response
 - CR,
 - CRI,
 - partial remission/response,
 - progressive disease,
 - refractory disease,
 - relapsed from CR or CRI or recurrent disease,
 - other
- minimal residual disease (MRD) evaluation for patients that achieved CR or CRI and the diagnose method for MRD evaluation
- Patient status description

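### SAP 8.7 in effect censors RFS and EFS at study enrolment, against the last-examination rule in SAP item 7 (EFS) and Protocol 9.7 (both); patients lost earlier with unrecorded events are counted as event-free

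*SAP*

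**What the plan says.** **RFS and EFS, SAP 8.7.** Both bullets say that patients without an event "are censored on the date they were last examined, study enrollment, last contact, whichever comes later".

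**EFS, SAP 8.7.2 item 7.** "Patients not known to have any of these events are censored on the date they were last examined". Enrolment and last contact are not mentioned.

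**RFS, SAP 8.7.2 item 10.** "the RFS analysis will consider the treatment end date until date of next treatment initiation or date of death, whichever comes first". No censoring date is given.

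**Protocol 9.7.** For EFS, "patients not known to have any of these events are censored on the date they were last examined"; the RFS bullet uses the same date. There is no censoring rule for OS.

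**OS, SAP 8.7.** "Patients not known to have died will be censored at study enrollment, last visit, last contact, whichever comes later". TTNT, in the same section, is censored at the earliest of similar dates.

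**End of data.** SAP 8.4.1 takes chart data from diagnosis up to what is available at enrolment. SAP 8.2.1 says: "The study period will comprise since diagnosis date (index date) until the study enrollment or death, whichever comes earlier". SAP 8.2.3, headed Follow-up Period and Censoring, ends follow-up either at the end of the study period or at the patient's last available information. It does not say which applies when.

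**Loss.** SAP 8.8 names early discontinuation, transfer to another institution and deaths missing from the chart as limitations. It does not connect them to the censoring rule.

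**The concern.** The SAP holds two EFS censoring rules, so the published EFS depends on which one is programmed. For RFS, SAP 8.7 has a rule and the analysis item has none.

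The rule in 8.7 also has a direction of bias. A patient last seen in month 4 and enrolled from the chart five years later would contribute five event-free years although only four months were observed. If that patient relapsed or died in between and the chart does not show it, the event is lost while the patient stays in the risk set. This raises the Kaplan-Meier curve, mainly in its tail.

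**Working it through.** **1. Which date the rule selects.** Chart data end at enrolment, so last examination and last contact cannot normally fall after it. The latest of the three dates is therefore enrolment.

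**2. How much unobserved time can be added.** Diagnosis runs from 01 January 2015 to 31 December 2019, and planned data collection from July 2021 to August 2022 (Protocol 6, which warns that dates may change). The shortest gap is end December 2019 to start July 2021, 18 months. The longest is January 2015 to end August 2022, 92 months or 7.7 years. For RFS the gap is shorter, because its clock starts at remission or treatment end.

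**3. Size, with no later event known.** The documents give no figure to reproduce, so all inputs here are assumptions:
- Event times are exponential with a long-term event-free fraction c. RFS: median 12 months, c = 0.25. EFS: median 6 months, c = 0.12.
- A share p of patients is lost independently of outcome, at an exponential time L with mean 12 months (rate μ = 1/12 = 0.0833).
- Nothing after loss is recorded.

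A lost patient whose event time T falls after L never shows an event. Enrolment is an administrative date, so the Kaplan-Meier curve estimates

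S*(t) = S(t) + p × Pr(L < T ≤ t), with

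Pr(L < T ≤ t) = (1 − c) × [(1 − e^(−λt)) − λ/(λ+μ) × (1 − e^(−(λ+μ)t))].

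*RFS at 36 months.* λ = ln(3)/12 = 0.0916. S = 0.25 + 0.75 × (1/3)³ = 0.2778. Pr = 0.75 × [0.9630 − 0.5235 × 0.9982] = 0.3303. At p = 0.20, S* = 0.2778 + 0.0661 = 0.344.

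*EFS at 36 months.* λ = −ln(0.38/0.88)/6 = 0.1400. S = 0.12 + 0.88 × 0.0065 = 0.1257. Pr = 0.88 × [0.9935 − 0.6268 × 0.9997] = 0.3229. At p = 0.20, S* = 0.1257 + 0.0646 = 0.190.

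The 5-year figures use the same formula at t = 60 (Pr = 0.3543 for RFS, 0.3282 for EFS). The medians solve S*(t) = 0.5.

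| | True | 5% loss | 10% loss | 20% loss |
|---|---|---|---|---|
| RFS median, months | 12.0 | 12.4 | 12.7 | 13.7 |
| RFS 3 years, % | 27.8 | 29.4 | 31.1 | 34.4 |
| RFS 5 years, % | 25.3 | 27.1 | 28.9 | 32.4 |
| EFS median, months | 6.0 | 6.1 | 6.2 | 6.4 |
| EFS 3 years, % | 12.6 | 14.2 | 15.8 | 19.0 |
| EFS 5 years, % | 12.0 | 13.7 | 15.3 | 18.6 |

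Simulation of 400,000 patients per scenario agrees to about 0.1 (months or percentage points). With no loss the rules coincide. Censoring at last examination returns the true values in this setting.

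**4. Other event-time models.** With plain exponential times and no long-term fraction, 20% nominal loss moves true medians of 6, 12 and 24 months to 6.8, 13.6 and 27.0.

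**5. If later deaths are known.** Simulation at 20% loss, further assuming that 80% of events are non-fatal and followed by death at a median of 6 months. Figures are 3-/5-year %, against true RFS 27.8/25.3 and EFS 12.6/12.0:

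| Rule | Later deaths known | RFS | EFS |
|---|---|---|---|
| Enrolment | half | 31.4/28.9 | 16.1/15.3 |
| Enrolment | all | 28.5/25.5 | 13.0/12.0 |
| Late deaths counted, lost survivors censored at last examination | all | 25.7/22.3 | 11.3/10.3 |

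The last row shows that last-examination censoring has its own, downward, bias when late deaths are recorded but late survival is not.

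**6. OS.** With a true median of 10 months and 15% long-term survivors, 20% loss and enrolment censoring give 25.9/23.4% at 3/5 years with no later deaths known and 18.6/15.5% with all known, against a true 18.5/15.4%.

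**The case against.** **The SAP may depart from the protocol.** This stands. Protocol 9.7 says "The SAP may modify the plans outlined in the protocol", so the difference from the protocol is not an error in itself. It does not resolve the conflict between SAP 8.7 and SAP item 7.

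**A reader might infer that the SAP reverses the protocol abstract**, which takes chart data "until the study enrollment, last visit, contact date or death, whichever comes earlier, will be assessed". That sentence sets which data are assessed. It is not a censoring rule, so the inference is not supported.

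**Enrolment is a legitimate cut-off.** It is, for patients still followed then. The fault is confined to those lost earlier.

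**Status at enrolment may be known.** SAP 8.7.1 describes enrolment by consent, with a waiver for deceased patients, and investigators may exclude charts with excessive missing data. Both could make the problem small. But Protocol 10.2 and SAP 9 request a waiver in general terms, and consent shows that a patient is alive, not free of relapse.

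**The planned summary hardly moves.** Items 7 and 10 name the median with its confidence interval, plus unspecified time categories; only OS has 1-, 3- and 5-year percentages. This largely stands: at 5 to 10% loss the median shifts by less than one month. The larger figures describe the tail of the plotted curves.

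**The model is not the SAP's working endpoint.** This stands. The SAP starts RFS at treatment end and counts next treatment as the event, and it dates non-fatal EFS events from treatment dates. The figures illustrate direction and order of size only.

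**Last-examination censoring is not always better.** This also stands. It assumes that loss is independent of outcome, which early discontinuation and transfer make doubtful. With 20% loss confined to patients without long-term event-free status and all deaths known, enrolment censoring gives RFS 28.7/25.5%. A last-examination rule that ignored deaths more than 3 months after it would give 31.1/29.0%, against a true 27.8/25.3%.

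**Conclusion.** The concern holds, with limits. The textual part needs no assumption: SAP 8.7 and SAP item 7 give different EFS censoring dates, item 10 gives none for RFS, and SAP 8.2.3 leaves the end of follow-up open.

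The bias is conditional. It is upward for RFS and EFS where patients are lost before enrolment and their later events are unrecorded, which SAP 8.8 expects. It is zero without loss, and near zero at 3 and 5 years if all later deaths are known. OS is affected only where alive status at enrolment is undocumented.

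The size cannot be set from the documents. Under the assumptions above it is 0.4 to 1.7 months in median RFS, 0.1 to 0.4 months in median EFS, and about 1.6 to 6.6 percentage points at 3 years for either endpoint. A reader might infer that the reported survival will be badly wrong; without a loss rate, the documents do not support that. The endpoints are secondary and descriptive, and the primary objectives are untouched. It should still be corrected before database lock.

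**What to change.** 1. **RFS and EFS.** Use one rule in SAP 8.7 and in items 7 and 10, the one already in item 7 and Protocol 9.7: patients without an event are censored on the date last examined. Align SAP 8.2.3 with it. Leave the endpoint definitions unchanged, so death from any cause remains an event.
2. **Sensitivity analysis.** Repeat RFS and EFS counting all known deaths and censoring every patient without an event at enrolment. Late deaths and comparable survivors are then followed to the same date. This is needed because of the downward bias in step 5 and because loss may depend on outcome.
3. **OS.** Censor at the latest date documented alive, and use enrolment only where alive status at enrolment is documented.
4. **Reporting.** Give the number of patients whose status at enrolment is undocumented and the number of deaths recorded after the last examination. State that the main result assumes loss is independent of outcome.

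**Cost.** SAP wording in 8.2.3, three bullets of 8.7 and two items of 8.7.2, plus minor programming. The CRF is not among the documents, so the team must check that it holds the last-examination date and vital status at enrolment. Late estimates will be less favourable and less precise.

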8.3.2. Outcomes

Primary outcomes

1. Description of demographic and clinical presentation characteristics at the moment of R/R B-cell ALL or AML diagnosis
2. Treatment description considering the front-line therapy and subsequent regimen(s) required for patients with R/R B-cell ALL and AML, including any systemic chemotherapy, target therapy, hematopoietic stem cell transplantation (autologous/allogenic), intrathecal chemotherapy and palliative management.

Secondary outcomes

3. Description of subtypes of AML and B-cell ALL based on the cytogenetic and molecular abnormalities, according to the WHO classification

Effective Date: 01Feb2022

4. Proportion of patients of each prognostic-risk group (favorable, intermediate, adverse) among newly diagnosed AML patients, based on cytogenetic profile
5. Description of the treatment standard from diagnosis to inclusion of R/R ALL patients
6. Description of clinically relevant events presented by AML and R/R B-cell ALL patients since treatment initiation until loss of follow-up or death from any cause;
7. The EFS will be the measure of time since diagnosis until failure to achieve complete remission (CR), or disease progression after CR, or death from any cause for both AML and R/R B-cell ALL patients;
8. The OS will be the measure of median time since diagnosis until death from any cause for both AML and R/R B-cell ALL patients;
9. The OS will also assess the proportion of AML and R/R B-cell ALL patients alive after 1, 3 and 5 years, if feasible, since treatment initiation;
10. For AML patients who achieved CR, the RFS will be the measure of time since the CR attainment until relapse or death from any cause;
11. For AML patients the response to induction and consolidation therapy will assess the proportion of patients who achieve CR, complete remission with incomplete hematological recovery (CRI), complete remission without minimal residual disease (MDR-), partial remission (PR), and progressive disease
12. For R/R B-cell ALL patients the response to the rescue treatment will access the proportion of patients with CR, complete remission without MRD-, PR, and progressive disease
13. Health care resource utilization description, considering the outpatient utilization, inpatient admissions, hospitalization length of stay, and concomitant medication prescription since diagnosis until the loss of follow-up or death from any cause.

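### RFS is defined as remission to relapse or death but computed as end of treatment to next treatment or death, so the quantity tabulated as RFS has no relapse event

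*SAP*

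**What the plan says.** The RFS bullet in SAP 8.7 holds two rules.

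- **Rule A**, for patients achieving CR or CRi: "considered as the date of achievement of a remission until the date of relapse or death from any cause".
- **Rule B**, for AML patients in CR or CRi at the end of treatment: "The RFS will be measured as the treatment end date until next treatment initiation or date of death, whichever comes first".

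The censoring sentence sits with rule A: "patients not known to have relapsed or died at last follow-up are censored". The censoring date is the latest of last examination, study enrollment and last contact.

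SAP 8.7.2 item 10, which specifies the output, has rule B alone: "the RFS analysis will consider the treatment end date until date of next treatment initiation or date of death, whichever comes first". It gives no censoring rule, and the Kaplan-Meier summary is still called RFS.

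SAP 8.3.2 item 10 keeps rule A, for patients in CR only: "the RFS will be the measure of time since the CR attainment until relapse or death from any cause". Protocol 9.7 also keeps rule A, for CR or CRi: "measured from the date of achievement of a remission until the date of relapse or death from any cause". Protocol 9.3.1.2 has rule A for CR only.

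SAP 8.7.6 lists RFS among the survival outcomes to be stratified by ECOG, cytogenetic risk, country and age, where data allow.

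**The concern.** The start date, the event set and the population all change between the definition and the computation, while the name stays the same. The SAP does not call rule B a proxy and does not say which rule governs.

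A reader of the report will take RFS as protocol 9.7 and SAP 8.3.2 define it, that is, time in remission until relapse or death. The tabulated number would be the time from end of treatment until someone starts another treatment or the patient dies. Relapse enters it only indirectly.

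The strata raise the same difficulty. A difference in this quantity between countries or age groups could reflect how often and how soon further treatment is given, as well as how long remission lasts. Protocol 7.4 gives limited access to targeted therapies as part of the study's rationale, so this confusion is a realistic one.

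**Working it through.** The documents give no RFS median, event count or rate, so there is no figure to reproduce. The check is a comparison of the texts, followed by dates worked by hand.

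**Step 1. The rules side by side**

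| Place | Start | Event | Population | Censoring |
|---|---|---|---|---|
| Protocol 9.3.1.2 | CR | relapse or death | CR | not given |
| Protocol 9.7 | remission | relapse or death | CR or CRi | no known relapse or death: last examined |
| SAP 8.3.2 item 10 | CR | relapse or death | CR | not given |
| SAP 8.7, rule A | remission | relapse or death | CR or CRi | no known relapse or death: latest of three dates |
| SAP 8.7, rule B | treatment end | next treatment or death | CR or CRi at treatment end | none of its own |
| SAP 8.7.2 item 10 | treatment end | next treatment or death | CR or CRi at treatment end | not given |

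Rule B is the only rule in the section that specifies the output, so it is the one that would be computed as the plan stands.

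**Step 2. What rule B leaves open**

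- *Which treatment's end starts the clock.* SAP 8.7.2 item 11 assesses response to induction and to consolidation. Rule B does not say whether the clock starts at the end of a phase or of a whole line.
- *What counts as next treatment.* Protocol 9.2.3 leaves transplant, induction, consolidation and maintenance out of the line count, but rule B speaks of treatment and not of a line. Planned therapy started in remission could therefore be read as an event.
- *Whether palliative management counts.* Protocol 9.2.3 defines palliative therapy as care other than cancer treatment. Protocol 9.3.1.1, protocol 9.3.2 and SAP 8.3.2 item 2 list palliative care or management under treatment.
- *How a relapsed, living patient without new treatment is handled.* This patient has no rule B event, and the censoring sentence does not describe the patient either, because a relapse is known.
- *Who is left out.* A patient who attained CR or CRi but was no longer in it at treatment end belongs to rule A and not to rule B. The number depends on how response is coded and could be zero.

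**Step 3. Dates worked by hand**

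All dates are assumed, in months on a common clock: CR at 2 and relapse at 10. Rule A = relapse − CR = 10 − 2 = 8 months, with an event, in every row. Rule B = next treatment − treatment end. Where there is no event, I assume censoring at last contact.

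| Course | Treatment end | Rule B |
|---|---|---|
| New treatment at 11 | 6 | 11 − 6 = 5, event |
| New treatment at 11 | 2 (same time as CR) | 11 − 2 = 9, event |
| No new treatment, alive at last contact at 14 | 6 | 14 − 6 = 8, censored |
| No new treatment, alive at last contact at 14 | 2 | 14 − 2 = 12, censored |
| Planned treatment in remission at 7.5, if it counts | 6 | 7.5 − 6 = 1.5, event |

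One relapse history gives 8 months under rule A. Under rule B it gives an event at 1.5, 5 or 9 months, or no event at all. Rule B can be shorter or longer, depending on matters that the SAP leaves undefined.

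Modelling a median would need the relapse rate, treatment duration, retreatment share and delay, and the share treated in remission. None of these is in the documents, so I give no modelled median.

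**The case against.** The best defence is that SAP 8.7 states a concept and then an operational rule, for EFS as well as for RFS. Rule B is written openly in two places, so a programmer would know what to compute. Protocol 9.7 lets the SAP modify the plan and names an amendment only for major changes to primary endpoints. RFS is secondary and descriptive. Protocol 9.3.2 lists response at the end of treatment, so remission and relapse dates may not exist and rule B may be all that can be computed. The table shells are in an attached file that is not reproduced, and its footnotes may explain the rule.

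Most of this stands. There is no missing amendment, and no error rate or sample size is affected. It does not remove the contradiction: three current SAP sections disagree on what RFS is, and none says that the computed version omits relapse.

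A reader might infer more than the documents support:

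- *That rule B simply repeats the time-to-next-treatment event.* That endpoint is "the time from the start date of the front-line therapy to the start date of a subsequent line of therapy". Rule B does not mention a line, whereas the EFS bullet beside it does. The equivalence is not established.
- *That EFS shows relapse being handled correctly.* Its rule counts a relapse "when treatment response was Refractory disease(5) or Relapsed from CR or CRI or recurrent disease(6) as treatment response". A patient in CR or CRi at treatment end has no such code for that treatment, so a later relapse off treatment is not shown to be captured there either.
- *That RFS will be overstated.* This would follow if next treatment came only after relapse. Treatment started in remission would push the other way.
- *That many relapsed patients will be carried as event-free, or that a known share of remitters is excluded.* The first depends on whether palliative management counts, the second on unstated response coding.

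**Conclusion.** The RFS plan is wrong as written. The rule that would be run yields a quantity other than the one named, because relapse is not an event in it, its start date differs and its population differs. Its censoring is unstated for the patients who matter most. CR only versus CR or CRi is a smaller inconsistency, already present between protocol 9.3.1.2 and 9.7.

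The conclusion rests on the wording of SAP 8.3.2, 8.7 and 8.7.2 and protocol 9.3.1.2 and 9.7, and on the assumption that SAP 8.7.2 item 10 governs the output. The direction and size of the effect cannot be determined from the documents, and the hand-worked dates show only that the rules can diverge either way. It should be fixed before the RFS tables are reported, but it touches one descriptive secondary endpoint and its strata and no primary objective.

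**What to change.** State one governing rule and use it in SAP 8.3.2, 8.7 and 8.7.2, settling CR versus CR or CRi at the same time. The rule depends on what the CRF holds, so check that first.

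- **If remission and relapse dates were collected:** analyse RFS from first CR or CRi to documented relapse or death, with the censoring rule in SAP 8.7. Use the start of next treatment only as a stated proxy where the relapse date is missing.
- **If they were not:** keep rule B for patients in CR or CRi at treatment end, but report it as *time from end of treatment to next treatment or death*. State that RFS as defined in protocol 9.7 and SAP 8.3.2 could not be estimated. Define which treatment's end starts the clock. Define what counts as next treatment, covering planned treatment in remission, transplant and palliative management. State the censoring rule, including for relapsed patients without new treatment. Report how many patients who attained CR or CRi are excluded.

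The cost is SAP wording, relabelling or reprogramming of one descriptive secondary endpoint, and one added count. Neither branch needs new data collection.
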